7.0 STUDY PARAMETERS

Patients will be randomized on a 1:1 ratio to TAU + internet or TAU+C-CHESS. Subjects will be stratified by gender, number of conditions and study site. It is anticipated that up to 330 patient subjects will be recruited at the participating clinics. Staff subjects will have access to C-CHESS for the duration of the study. Patient will have access to C-CHESS for 12 months.

8.0 STATISTICAL CONSIDERATIONS

Power analyses for primary and secondary outcomes. Our power analysis was based on Elder Tree pilot data and other studies that examined the impact of behavioral interventions on single chronic conditions.⁹⁵ A meta-analysis⁹⁶ of self-management interventions found significant effects on HbA1c for diabetics ($d = .36$), and on systolic blood pressure among hypertensives ($d = -.39$). Other studies found a moderate effect size ($d = .61$) on pain behavior⁹⁷ and a small effect on number of primary care visits ($d = .28$) when patients attended self-management and peer-support meetings.^{98,99}

Because effect sizes vary for interventions of chronic conditions, we want our expected effect sizes to be conservative and yet clinically meaningful. We therefore chose an effect size of $d = .40$ for our primary

outcomes (quality of life and primary care use) as well as individual condition measures (secondary outcomes) and the composite score based on them. Adequate power ($1-\beta = .80$, two-tailed $\alpha = .05$) would require a final sample of $N=200$ patients (100 per arm).¹⁰⁰ Since we will examine 4 clusters, with 3 conditions per cluster, we will need 132 per arm. Assuming 20% attrition, we will recruit $N=330$ patients (33 per arm per clinic). This should also be sufficient for detecting similar effect sizes (at a power of $1-\beta = .80$) for condition-specific changes in diabetes,¹⁰¹ hypertension,¹⁰² and arthritis.¹⁰³ The literature is less clear in hyperlipidemia but 50% of patients are non-adherent to statins,¹⁰⁴ and statins have a high effect size,¹⁰⁵ so our goal may be achievable.

Power for mediation and moderation analyses. Power for detecting parameter changes in the structural model was estimated using a procedure of Satorra and Saris¹⁰⁶ that approximates the non-central chi-square distribution. A total N of 220 patients will provide adequate power ($> .80$) to detect a group difference in a parameter by moderate .4 standard deviations. With an N of 264 in our primary analysis, we are confident our secondary analysis will have adequate power.

Impact on power calculations of adding attention control and the Clinician Report. We are using a placebo comparison group to remove the Hawthorne effect, not to contribute to managing chronic conditions. Conversely, the addition of the Clinician Report to the Elder Tree system upon which C-CHESS is based should have a positive effect. We compared CHESS to CHESS+CR in a lung cancer RCT and found statistically and practically significant improvement in symptom distress by adding the CR. Overall, we believe this change will make our power analyses conservative.

Missingness

In previous work, we completed 85% of interviews at 4, 8, and 12 months and kept missing data on core interview items to about 2%; we expect these rates in this study. In primary care, data are not likely to be missing at random (i.e., the probability that data are missing relates to what the data would have been had the data been observed). Because this may lead to biased parameter estimates for our models, we will identify missing data patterns and use pattern-mixture modeling to test the sensitivity of our longitudinal intervention analysis to missing data assumptions,^{107,108} and conduct other sensitivity analyses after imputing missing data with a range of clinically plausible values based on explicit assumptions for the missing data (e.g., best-case, worst-case; with and without multiple imputation).^{109,110}

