Elder Tree was tested in an RCT involving 399 older adults from 3 Wisconsin counties (urban, rural, and suburban). We followed participants for 18 months and assessed outcomes at 0, 6, 12, and 18 months.⁴¹

Elder Tree subjects were asked to identify their chronic conditions so we could examine data about the impact of Elder Tree on those with MCCs. We identified 66 older adults with at least 3 of the 4 target MCCs. Subjects' conditions included (in addition to hypertension, hyperlipidemia, diabetes, and arthritis) cancer, pain, depression, anxiety, heart disease, obesity, osteoporosis, and falls. The Elder Tree RCT included 4 measures we plan to use in this study: health-related quality of life, use of primary care services, relatedness (feeling connected with others), and number of symptoms. For the clusters we propose to study in this project, we found moderate (0.4+) to large effect sizes, all favoring Elder Tree, with 2 exceptions in which small effects favored Elder Tree. These data helped us conduct power analyses and estimate sample sizes for the C-CHESS RCT.

Effect sizes from Elder Tree data					
Chronic Condition Clusters	n Control/ Elder Tree	Quality of Life	Fewer Primary Care Visits	Relatedness	Fewer Symptoms
Hypertension/hyper-lipidemia/arthritis	17/21	0.20	0.61	0.56	0.56
Hypertension/hyper-lipidemia/diabetes	11/10	0.40	0.66	0.36	0.45
Hypertension/arthritis/diabetes	16/11	0.96	0.71	0.52	0.53
Hyperlipidemia/arthritis/diabetes	14/14	1.09	0.56	0.91	0.75

As mentioned above, C-CHESS will add to Elder Tree the Clinician Report (CR), which alerts clinicians when thresholds are reached in a patient's status. We used a similar system in a lung cancer RCT comparing CHESS to CHESS+CR. The addition of the CR to CHESS improved ($p < .001$) symptom distress by over 100% (26.2% improvement with CHESS vs. 53% in those with CHESS+CR; $n = 71$ vs. 68 respectively). These statistics are averaged across 6 observations over 12 months. We expect the proposed CR to increase the effects of C-CHESS compared with Elder Tree.

Innovation: The intervention is innovative for the following reasons.

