6.0 MEASUREMENT OF EFFECT

All scales being used in this study have good psychometric properties with similar populations. Listed below are the factors to be measured and measurement instruments with references to validation studies.

Quantitative analyses. Two types of analyses are planned: 1) a general, whole-sample analysis of outcomes not specific to any condition, and 2) analyses of condition-specific outcomes that permit integration across condition categories.

The first, general outcome category includes quality of life and primary care use which will be assessed with the same measures and same metrics regardless of conditions.

The second type of analysis is for condition-specific outcomes: mm Hg for hypertension, mg/dL for hyperlipidemia, HbA1c for diabetes, and pain for arthritis. These outcomes will be analyzed in 2 ways. In one approach, scores on each measure will be transformed to Z scores and combined to create the composite score across all 5 outcomes, which will constitute an improper linear model with unit weighting; this is a secondary outcome. Thus, patients will be compared based on the pooled composite. Because we believe that change in the composite will reflect specific conditions and combinations, these factors will be entered as covariates in separate analyses to determine whether particular conditions or combinations of conditions are significantly related to the magnitude of treatment effects on the composite. Because patients often have more than 3 chronic conditions, we will code for the presence or absence of other common chronic conditions (e.g., cancer, pain, depression, anxiety, falls, heart disease, diabetes, and osteoporosis). The particular combinations involved will be entered as dummy variables. The second approach to the analyses of condition-specific outcomes will involve examining condition-specific outcomes individually, with only those individuals in the C-CHESS and comparison groups who have the pertinent diagnosis contributing data to the analysis (e.g., only those with diabetes will contribute data to the analyses involving HbA1c). The analytic approach to symptoms would be similar to the approach to the condition-specific tests. We will set a threshold for inclusion in the composite, and use as individual dependent variables the symptoms that occur in $\geq 10\%$ of the sample.

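### The .80 power stated for condition-specific outcomes needs about 75% of completers to have each condition; the pilot mix gives 67% for diabetes (power .75), and the current eligibility list does not secure 75%

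*Combined protocol and SAP*

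**What the plan says.** Section 8.0 (Statistical Considerations) sets d = .40 for the primary "outcomes (quality of life and primary care use) as well as individual condition measures (secondary outcomes) and the composite score based on them". At two-sided alpha .05 and power .80 it arrives at 100 per arm. It then moves to 132 per arm: "Since we will examine 4 clusters, with 3 conditions per cluster, we will need 132 per arm". With 20% attrition this becomes 330 recruited, and 264 is given as the number in the primary analysis.

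Of this sample size the section says: "This should also be sufficient for detecting similar effect sizes", at power .80, for diabetes, hypertension and arthritis. Hyperlipidemia is treated more cautiously.

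Section 6.0 (Measurement of Effect) defines the condition-specific analyses as run "with only those individuals in the C-CHESS and comparison groups who have the pertinent diagnosis contributing data to the analysis".

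The clusters appear under Preliminary data: "We identified 66 older adults with at least 3 of the 4 target MCCs". The table there lists the four possible triples of hypertension, hyperlipidemia, arthritis and diabetes. Section 2.0 (Selection of Subjects) now requires at least three conditions from a list of ten. The opening summary names five conditions.

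**The concern.** The condition-specific tests use subsets, but section 8.0 states their power without giving any subset size. The step from 100 to 132 rests on the four-condition cluster structure, no condition share is written down, and eligibility has since been widened to ten conditions.

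The individual condition outcomes are named secondary outcomes in section 1.0. If fewer patients have a condition than the sample size assumes, a null result (for HbA1c, say) will be read against a promised .80 that the design did not provide.

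**Working it through.** **Inputs.** From section 8.0: d = .40, two-sided alpha .05, power .80, 132 evaluable per arm, 20% attrition, and a cited effect of d = .36 for HbA1c and .39 (absolute) for systolic pressure. From Preliminary data: cluster sizes (control plus Elder Tree) of 38, 21, 27 and 28 among 66 people. From section 7.0: 1:1 allocation.

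**Reproducing the plan's figures.** The number per arm is 2(1.960 + 0.842)²/d² = 2(1.960 + 0.842)²/0.16 = 98.1, rounded up to 99 (99.1 by the t-test). The plan's 100 agrees.

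The four clusters are the four triples of four conditions, so each condition is in three of them. If the clusters are equally filled and each patient has exactly three conditions, each condition is present in 3/4 of patients. Then 99/(3/4) = 132, and 264/(1 − .20) = 330. Both stated figures reproduce. The protocol does not write this step out, so it is an inferred derivation. A split of alpha over three tests also lands close, at 132.3.

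**Power at 132 per arm.** Power is approximately Φ(d√(n/2) − 1.960); the results below are t-based.
- Whole sample, n = 132, d = .40: .90.
- One condition at a 75% share, n = 99: .80, with no margin.

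**Condition shares implied by the pilot.** Assume each cluster count covers everyone with that triple. A person with all four conditions is counted four times, and a person with exactly three is counted once. With x people having all four, 38 + 21 + 27 + 28 = 114 = 66 + 3x, so x = 16 and 50 have exactly three.

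The numbers with exactly each triple are 38 − 16 = 22 (no diabetes), 21 − 16 = 5 (no arthritis), 27 − 16 = 11 (no hyperlipidemia) and 28 − 16 = 12 (no hypertension). Subtracting each from 66 gives the number with the condition:

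| Condition | Pilot share | Per arm, of 132 | Power at d = .40 |
|---|---|---|---|
| Diabetes | 44/66 (67%) | 88 | .75 |
| Hypertension | 54/66 (82%) | 108 | .83 |
| Hyperlipidemia | 55/66 (83%) | 110 | .84 |
| Arthritis | 61/66 (92%) | 122 | .88 |

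For diabetes: .40 × √44 − 1.960 = 0.693, giving .756 by the normal approximation and .751 by the t-test. At d = .36: .36 × √44 − 1.960 = 0.428, giving .666 and .661. Hypertension at the cited .39 gives .81.

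**Shares under wider eligibility.** The documents give no condition shares for the current list, so these are assumed values. The same equal-filling logic gives 60% for three of five conditions and 30% for three of ten.

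| Assumed share | Per arm | Power at d = .40 |
|---|---|---|
| 75% | 99 | .80 |
| 60% | 79 | .71 |
| 50% | 66 | .63 |
| 30% | 40 | .42 |

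The 30% row is a low illustration, not a forecast: patients may have more than three conditions, and some conditions on the list are commoner than others.

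**The case against.** **The sample size itself is sound.** A reader might infer that 132 is an arithmetic error because no cluster calculation produces it. The documents do not support that: 99/(3/4) = 132 uses both halves of the cluster sentence, and 264/.80 = 330 follows. Whole-sample power is .90. This part of the objection stands in full.

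**No alpha split is planned.** Someone might read the four clusters as four tests at .05/4, which would need 141 per arm and leave power of .77 at 132. Section 8.0 states alpha .05, and no passage divides it over clusters. That shortfall is measured against a rule the plan never set.

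**No within-cluster test is promised.** The pilot cluster shares would give 76, 42, 54 and 56 per arm and power of .69, .44, .54 and .55. But section 6.0 analyses the composite over all patients, with combinations entered as dummy variables, and the individual outcomes by diagnosis. Section 8.0 claims no power within a cluster.

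**Diabetes misses narrowly, and the model may recover it.** The analysis adjusts for baseline. With baseline correlation r the effective effect is d/√(1 − r²). At 88 per arm .80 needs an effect of about .425, so r of about .34 suffices at d = .40 (√(1 − (.40/.425)²)) and about .53 at d = .36. Loss may also be below 20%, since laboratory values come from the health record: with no loss, 165 × 2/3 = 110 per arm and power is .84 at d = .40. These points are fair, but the plan states no baseline correlation and applies 20% attrition throughout. They may be added as stated assumptions; they do not support the claim as it stands.

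**Conclusion.** The point holds in a limited form. On the plan's own two-sample calculation, .80 for a condition-specific outcome depends on an unstated 75% share. The pilot mix misses that share for diabetes, with power of .75 at d = .40 and .66 at the cited d = .36. It meets it for hypertension and arthritis at d = .40. The present rule of at least three of ten conditions no longer has the three-of-four structure that yields 75%, so no single .80 can be stated for all three conditions.

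The diabetes figure assumes that the pilot cluster counts are complete and that the trial resembles the pilot. The figures for 60%, 50% and 30% are assumed shares. Only secondary outcomes are affected.

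**What to change.** Keep N = 330 and amend section 8.0 as follows.

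1. State that 132 evaluable per arm gives about .90 power at d = .40 for one whole-sample test at two-sided alpha .05.
2. Replace the cluster sentence with the actual derivation of 132, including the assumed condition share. If that derivation is 99/.75, say so.
3. Replace the blanket .80 with a table of power by condition over a stated range of shares under the current eligibility list, with any baseline correlation given as an assumption.
4. For conditions below .80, report the effect with its confidence interval and do not read a null result as absence of effect. The condition-specific outcomes remain hypothesised secondary outcomes; they need not all be relabelled as estimation only.

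The cost is a few sentences and one table, with no extra patients. Some stated secondary power figures become less favourable.

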1.0 STUDY OBJECTIVES

This project will test the use of an eHealth intervention called C-CHESS, to modify health behaviors and improve health outcomes in older adults with comorbid chronic diseases and health conditions.

Aim 1 Refine C-CHESS, using feedback from patients and primary care clinicians.

Aim 2 Conduct a randomized clinical trial to test 4 hypotheses:

1. *Primary outcomes:* Patients assigned to TAU+C-CHESS will have better quality of life and less primary care use (fewer visits) than those assigned to TAU+Internet.
2. *Secondary outcomes:* Patients assigned to TAU+C-CHESS will have improved composite scores; improved individual condition outcomes (mm Hg for hypertension, mg/dL for hyperlipidemia (LDL), HbA1c for diabetes, and pain for arthritis); and fewer symptoms from a list than patients assigned to TAU+Internet.
3. *Mediators:* Patients assigned to TAU+C-CHESS will have, compared with patients assigned to TAU+Internet, greater adherence to medications and appointments as well as improved competence,

relatedness, and autonomy.

4. *Moderators:* Improvements in primary outcomes for TAU+C-CHESS vs. TAU+Internet will be greater for women than men, those ≥ 75 vs. 65 to 74, and those with 3-5 chronic conditions vs. 6+.

Aim 3 Analyze data from the RCT and publish results.

Exploratory questions:

- Does C-CHESS reach a large proportion of targeted patients, get a large proportion of targeted clinicians to use C-CHESS, get a large proportion of patients to regularly use C-CHESS, and maintain that performance over time)?
- Does the use of specific C-CHESS services affect outcomes?
- Does the use of C-CHESS affect other health service use?

Primary Aim

Patients assigned to TAU+C-CHESS will have better quality of life and fewer primary care visits than those assigned to TAU+Internet.

C-CHESS will contain the Clinician Report to make it easier for PCPs to respond to important patient changes, pilot data suggested that primary care visits could be reduced. Reducing the number of primary care visits will both lessen provider burden and ultimately reduce healthcare costs.

Secondary Aim

Patients assigned to TAU+C-CHESS will have improved composite scores; improved individual condition outcomes (mm Hg for hypertension, mg/dL for hyperlipidemia (LDL), HbA1c for diabetes, and pain for arthritis); and fewer symptoms from a list than patients assigned to TAU+Internet.

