Participants who do not already own a computer will be receiving a laptop as part of the study. The laptop has an administration interface that allows our technical team to access devices remotely if a participant calls tech support or reports a problem. If a participant loses their laptop or installs something that is causing problems, we have the ability to remotely wipe the device, lock it down, restore the operating system and/or run a security check. We can also do security updates remotely to make sure patches are up to date on each laptop and security software has not been disabled by the user.

Patient Randomization: Once informed consent and baseline measures have been obtained from patients, they will be randomized to either the experimental (TAU + C-CHESS) or control (TAU + Internet) group, stratified on gender, clinic site, and number of chronic conditions (3-5 vs. 6+). Patients who are in the experimental group will be further randomized into two groups, one will be asked to identify a health outcome to track and share with their physician using the Clinician Report and the other group will not.

When baseline assessment and consent are complete, the researcher will enter the participant number and randomization data into a randomization spreadsheet. The interviewing researcher, once informed of group assignment, will provide setup and training.

The research staff will train participants to use C-CHESS and customize it (e.g. by health condition) during a home visit. Participants will be asked to check in regularly, initially at a daily rate with frequency of at least weekly over the course of the study.

Patient Qualitative: Data will be gathered via an interview at 3 times from 6 patients at each of the 5 clinics (N=30). Each interview is expected to take 30-60 minutes and will take place either in-person at a place of the subjects choosing or via phone.

Recruitment: Participants will be identified through a consent form opt-in question and demographics as reported on the baseline survey. We will seek a mix of genders and number of chronic conditions. We will also look at C-CHESS use data to find a mix of users and non-users. We will contact potential participants by messaging them through the C-CHESS application or phoning them.

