Data collection

Participants will be tracked for a total of 18 months; 12 months with access to the interventions and 6 months for follow up. Data will be collected from: electronic health records (EHR), participant surveys (at months 0, 6, 12, and 18), and C-CHESS data.

Participant EHR data will be shared by SMPH or MUSC with the study team via RedCap. An employee designee of each site will retrieve from files or receive a passworded spreadsheet of participant study id via either encrypted email or Box.

Each participant survey is expected to take 20-30 minutes and will assess: demographic, quality of life, resilience, pain, medication adherence, and health care utilization. Surveys will be mailed to participants with a stamped return envelope included.

Participants will be paid \$10 for each completed survey.

Survey data will be entered into REDCap (Research Electronic Data Capture). The UW study coordinators conducting surveys will be blind as to group assignment.

Qualitative participant data will be gathered via interviews with 30 participants conducted 3 times per person over the course of the study. Each interview is expected to take about 30-60 minutes and will take place either in-person or via phone.

Participant focus group data will be gathered 2 times during the study and will be used for system and content enhancement and improving the user interface. Focus groups will contain 3-7 unique participants, will last 1-2 hours and will be conducted in-person.

Use data. C-CHESS use data will be collected in time-stamped log files, including when a patient accessed C-CHESS, service(s) used, duration of use, pages viewed, messages posted vs. received, and the content of messages.

Staff subjects. Clinical staff will be consulted in the design and implementation of the Clinician Report (CR) feature of the website. They will also be asked as the study progresses about how they are using the CR, what they find helpful, and their opinions about the sustainability of C-CHESS in their organization. These discussions will be informal and participation is optional.

Unanticipated Events

Should any unanticipated problems arise the UW research team will work with the HS IRB to immediately address the problem, using the following guide:

What Event is Reported	When is Event Reported	By Whom is Event Reported	To Whom is Event Reported

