This analysis plan should allow us to examine treatment-related change with regard to: 1) condition-specific clinical outcomes; 2) general outcomes reflecting disease coping and burden; and 3) condition-specific clinical outcomes when modeled as a composite score that reflects status with regard to the 5 major conditions.

Effectiveness of TAU+Internet vs. TAU+C-CHESS. We will use separate mixed-effects models to evaluate the primary and secondary outcomes. Each model will include fixed effects for TAU+Internet vs. TAU+C-CHESS, time (6, 12, and 18 months), and the arm-by-time interaction, including the baseline assessment of each outcome as a covariate. We will also determine whether clinic exerts main effects or interacts with the treatment condition. The latter will test the consistency of C-CHESS effects over different clinics and whether data can be pooled across sites. The initial intercepts will be modeled as random variables to estimate variance and covariance of intervention effects at the different fixed occasions, and across and between patients. These models account for dependence among successive observations made on the same patient and use all available data (not just complete cases). We will conduct treatment time contrasts between and within groups to test time-based effects, with our primary analysis focused on the C-CHESS effect at 12 months. Generalized linear mixed-effects models will be used for the count outcomes addressing primary care use. If a count outcome has sufficient variability, Poisson regression will be used; if not, the outcome will be coded as dichotomous (some service use vs. none) and logistic regression will be used.

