Mediation. We will test 4 potential mediators of the intervention's effect on the primary and secondary outcomes. We will also test whether the condition-specific and composite secondary outcomes mediate the intervention's effect on the primary outcomes. Mediation will be tested by individually testing the 2 paths in the indirect effect and will conclude statistical significance only when the null hypothesis of no effect is rejected for both paths in the mediational pathway. To limit the number of analyses, we will use Bolt's approach⁹⁴ of first using a screening approach that examines only mediational models with outcomes and potential mediators significantly affected by the intervention. We will then use separate univariate models to determine which mediate the intervention effect on given outcomes. If 2 or 3 mediators are found, we will simultaneously enter all the significant mediators into the same model. If 4 mediators are found, we will enter the 'strongest' mediator first and then test whether adding remaining mediators shows significant mediational effects.

Moderation. A moderation model holds that the strength of the relation between intervention and outcomes is a function of the level of other variables and tries to explain under what conditions the treatment model functions. We will test whether gender, age (65-74 vs ≥ 75), and number of chronic conditions (3, 4, or 5) moderate the effect of the intervention on outcomes. Also, when standardized composites are used as the dependent variable, type of chronic condition will be used as a moderator to determine if the composite varies meaningfully by condition. Participants will list changes in chronic conditions at 6 and 12 months.

Moderated mediation. Although both constructs of mediation and moderation are of interest in our research, the process is more complex than just these factors. For example, a variable (e.g., relatedness) may act as a stronger mediator for 1 subgroup (e.g., women) than another (e.g., men).

Qualitative analyses. Through 3 interviews we will gather qualitative data from clinic staff to provide additional insights into their use of the CR.

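### The power above .80 stated for moderation at N=220 is tied to no named contrast, and is not shown to hold for the .4 SD treatment-by-moderator difference in Hypothesis 4

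*Combined protocol and SAP*

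**What the plan says.** Section 8.0 treats power for mediation and moderation in one short paragraph. It cites a Satorra–Saris calculation in a structural model and reports: "A total N of 220 patients will provide adequate power ($> .80$) to detect a group difference in a parameter", the size being .4 SD. It then concludes: "With an N of 264 in our primary analysis, we are confident our secondary analysis will have adequate power". The model, parameter, groups compared, degrees of freedom and time point are not given. Nothing else in the documents states power for moderation.

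Hypothesis 4 in section 1.0 (Study Objectives) is the moderation hypothesis: "Improvements in primary outcomes for TAU+C-CHESS vs. TAU+Internet will be greater for women than men", and likewise for age 75 and over against 65–74, and for 3–5 conditions against 6 or more.

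Section 6.0 (Measurement of Effect) describes the outcome models as "including the baseline assessment of each outcome as a covariate", "with our primary analysis focused on the C-CHESS effect at 12 months". Its Moderation paragraph sets no time point and says the trial will test whether "number of chronic conditions (3, 4, or 5) moderate the effect of the intervention on outcomes". The stratification in section 3.0 (Registration Procedures) uses 3–5 against 6 or more, as Hypothesis 4 does.

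**The concern.** Moderation asks whether the arm difference differs between two kinds of patient. It is a difference of two differences. With equal arms and equal subgroups, its standard error is twice that of the overall arm difference in the same patients. A .4 SD effect that a two-group comparison detects with power just above .80 at N=220 will therefore not be detected with that power as an interaction, unless something else removes much of the variance.

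Hypothesis 4 is one of four hypotheses that the trial sets out to test. Someone using section 8.0 to judge a null moderation result could take the chance of finding a .4 SD subgroup difference to be over .80, and so read the null as evidence that the effect is uniform.

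**Working it through.** **Inputs from the documents.** Total N of 220 and 264 (330 × .80 = 264), .4 SD and two-tailed .05 (section 8.0, where alpha is stated for the primary and secondary outcomes); 1:1 allocation (section 7.0); baseline covariate and visits at 6, 12 and 18 months (section 6.0).

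**Assumptions.** The same alpha applies to moderation. The outcome is continuous. The moderator has two equal levels. The baseline covariate is kept in the moderation model. The .4 is in units of the raw outcome SD. The baseline–outcome correlation r is not in the documents; .5 to .7 is used, with .8 as a sensitivity value.

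**Step 1: the stated figure.** For two groups of 110, SE = √(2/110) = .1348. Then .4/.1348 = 2.967, and power = Φ(2.967 − 1.96) = .843. The 1-df non-central chi-square with λ = 220 × .4²/4 = 8.8 also gives .843. At N=264 the two-group power is .901.

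The figure also reproduces as a difference of .4 in a treatment path coded ±1. There the arm effect is twice the path, so .4 means a .8 SD difference in arm effects.

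**Step 2: the treatment-by-moderator contrast.** With four equal cells, SE = (4/√N) × √V and power ≈ Φ(.4/SE − 1.96).

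- One visit with the baseline covariate: V = 1 − r².
- Mean of three visits with the covariate: V = (1 + 2c)/3 − r², where c is the correlation between follow-up visits. Compound symmetry means c = r.

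Example: N=220, 12 months, r = .5. SE = (4/14.83) × √.75 = .2336; .4/.2336 = 1.713; power = Φ(−.247) = .40.

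| Case | V | N=220 | N=264 |
|---|---|---|---|
| 12 months, no covariate | 1 | .32 | .37 |
| 12 months, r = .5 | .750 | .40 | .47 |
| 12 months, r = .7 | .510 | .55 | .62 |
| 12 months, r = .8 | .360 | .70 | .77 |
| Three visits, r = c = .5 | .417 | .63 | .71 |
| Three visits, r = c = .7 | .310 | .76 | .83 |
| Three visits, r = c = .8 | .227 | .88 | .93 |
| Three visits, r = .5, c = .6 | .483 | .57 | .65 |
| Three visits, r = .7, c = .8 | .377 | .68 | .75 |

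An ANCOVA simulation with an interaction term (8,000 trials per cell) agrees. At 12 months with r = .5 and .7 it gives .395 and .546 (N=220) and .462 and .627 (N=264). For three visits under compound symmetry it gives .627 and .756, and .706 and .830.

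**Step 3: what .80 would take.** At 12 months r must be about .85 (N=220) or .81 (N=264). For the three-visit mean under compound symmetry, within r of .3 or more, it must be about .74 or .66. At N=264 the 12-month difference detectable with .80 power is 2.80 × SE: .60 SD at r = .5 and .49 SD at r = .7.

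**Step 4: unequal split.** With 30:70 the factor 4/√N becomes √(4/(.3N) + 4/(.7N)) = 4.36/√N. For r = .5 to .7, 12-month power is .348 to .478 (N=220) and .405 to .550 (N=264).

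**The case against.** The strongest reply is that the sponsor's parameter is unknown. The sentence speaks of a parameter in a structural model, the figure reproduces on at least two readings, and an ANCOVA interaction is a reading supplied here. That stands. A reader might infer that the sponsor made an arithmetic error; the documents do not support this, because they do not say what was calculated. But neither reading that gives .84 is a .4 SD subgroup difference in treatment effect, so the sentence does not establish power for Hypothesis 4.

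A second reply is that r, the split and the visit correlations are assumed, and that some cases pass .80. This also stands. A reader might infer that moderation cannot reach .80 at all. That goes too far: the Moderation paragraph fixes no time point, and the three-visit mean at N=264 reaches .83 at r = .7. That case, however, needs follow-up visits to correlate no more with each other than with baseline. It also needs the full difference to persist to month 18, although the design is "12 months with access to the interventions and 6 months for follow up".

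Third, Hypothesis 4 is directional. A one-sided .05 test raises 12-month power for r = .5 to .7 to .53–.67 (N=220) and .59–.74 (N=264), still below .80. It raises the three-visit mean under compound symmetry to .74–.85 and .81–.90. The only alpha in the documents is two-tailed.

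Finally, the figures cover a continuous outcome such as quality of life. Hypothesis 4 also concerns primary care visits, which section 6.0 models by Poisson or logistic regression. Nothing here quantifies power for that outcome.

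**Conclusion.** The point holds as a gap between the stated power and the hypothesis it appears to serve. Section 8.0 does not show power above .80 for a .4 SD treatment-by-moderator difference. At 12 months, the focus of the primary analysis, power is about .40–.55 at N=220 and .47–.62 at N=264 for r = .5 to .7, and it stays below .80 even at r = .8. Averaging over three visits reaches .80 only under favourable correlations. These figures rest on the assumptions listed in the working, of which the equal split is the most favourable; an unequal one lowers power.

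A reader might also infer that the trial is too small. The documents do not support that from this point: the sample size was set for the primary and secondary arm comparisons, which this leaves untouched.

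The differing levels of the number-of-conditions moderator are a separate inconsistency. It matters here because power cannot be stated for levels that are not settled.

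**What to change.** - **Mediation.** Keep a power statement, since the present sentence is the only one there is, and name the path it refers to.
- **Moderation.** Add a separate statement giving the contrast, time point, moderator split, alpha and baseline–outcome correlation. Take the correlation from the sponsor's Elder Tree trial, which measured quality of life at 0, 6, 12 and 18 months, or show a range. Possible wording for a continuous outcome: with 264 completers and an equal two-level moderator, power (two-sided .05) for a .4 SD treatment-by-moderator difference at 12 months is about .47–.62 if baseline correlates .5–.7 with the outcome; the difference detectable with .80 power is about .60 SD (r = .5) to .49 SD (r = .7).
- **Visit average.** If moderation is to be tested on the mean over visits, say so and give that figure with its correlation assumptions between visits.
- **Primary care visits.** Say that these figures do not cover this outcome, which is modelled as a count or as dichotomous.
- **Number of conditions.** Reconcile 3–5 against 6 or more (sections 1.0 and 3.0) with 3, 4 or 5 (section 6.0), so that the statement refers to the levels tested.

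The cost is wording and a short recalculation. No patients or data are added. The only downside is a less favourable stated power.
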